In exploratory work supported by NIMH (R21MH109374), we used Internet-of-Things (IoT) and mobile technologies to develop a “smart” HBST kit that monitors when recipients open the kits, enabling an HIV test counselor to reach out to provide timely follow-up phone counseling/referral. The system (called “eTEST”) uses a Bluetooth low energy beacon (Estimote LocationTM beacon) with an ambient light sensor that is placed inside each test kit’s enclosure (see Figure 1). Smartphone applications (both iOS and Android) installed on recipients’ phones then monitor the proximity of the beacon to the phone and the amount of light reaching it (>1 lux) to automatically determine whether the recipient has opened the test enclosure. When these conditions are met, the app then updates a Structured Query Language (SQL) database on a central server and sends push notifications to users reflecting that they should expect a call from a counselor. The SQL database also issues notifications to a team of paraprofessional HIV test counselors, who place follow-up phone calls to users to conduct post-test counseling and provide referrals to users for other services (e.g., STI testing, PrEP consultation). The system requires no intervention from users to work, and successfully detects kit opening events even when the app is in the background, has been “killed,” or the user’s device is in sleep mode. “Pings” to the central server from the eTEST app also allow the HIV test counselors to monitor whether specific users have the app on their devices. See Fig. 2 for eTEST system flow.

In our small pilot study, we enrolled 73 participants, 92% of which have been retained to date. Response rates to online surveys have been excellent, with an average monthly completion rate of 94% ( $SD=4.3$ , 86%- 100%). Of those in the eTEST group, 75% have kept the app downloaded on their phones over the average of 5 months they have been enrolled so far. All but two of these participants were contacted and successfully re-downloaded the app to continue the study. The eTEST system has successfully detected 91% of opening events among eTEST

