### **Quarterly online questionnaires.**

Participants will also complete online questionnaires each quarter during the 12-month study period, which will be staggered and assigned one month after each testing interval to minimize possible conditioning effects. These surveys will assess HIV testing since the last study assessment, including whether they tested, how/where they tested, what their results were, whether each test was associated with PrEP care, or reasons for not testing. This approach will allow us to track contamination across conditions, or the extent to which those assigned to the control condition used a HBST or those in HBST conditions tested at a clinic. Questionnaires will also assess whether participants were referred for additional prevention services (e.g., STI testing, HIV risk reduction counseling), and whether they received these services since the last survey. Items will also assess whether participants consulted with a medical provider about PrEP in the last month, and if so, their provider's information and whether they were prescribed PrEP. Finally, as a compliment to passive app data, questionnaires will also assess app usage. These surveys will also assess constructs relevant to the behavioral, emotional, and social effects of HBST, including sexual risk behavior (online Timeline Follow Back), emotional health (PANAS-X), health empowerment, and social support. Finally, these surveys will also assess financial strain, insurance, housing instability, stigma, and medical mistrust, given evidence that these factors may be barriers to testing.

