## Planned Analyses

Analyses will be conducted in Year 5. To evaluate Aim 1(a), we will use factorial logistic regression to test whether rates of having completed any HIV test over the 12 month study period (assessed via self-report and/or clinic records) differ by study condition. Condition, study site (and their interaction) and other relevant covariates will be entered as predictors, allowing us to explore whether each condition's effects differ by study site. To explore the effects of study condition on regular HIV testing, we will use a generalized estimating equation (GEE) for repeated, binary outcomes, specifying whether participants tested during each 3-month study period as the focal outcome. A logit link function and independent correlation structure will be specified, with study condition, site, and relevant covariates as predictors, to test whether the odds of testing differ across time period, condition, and site. GEEs are a fitting approach for studies in which correlations between repeated measures variables are to be controlled, rather than a central focus of the analysis. For all models of **HIV testing** outcomes, a covariate reflecting whether a given participant had initiated PrEP (and when, for longitudinal models) will be added to each model, since these individuals are required to test for HIV quarterly as a part of ongoing PrEP care. Doing so will allow us to estimate the effects of study arm on HIV testing among those who did not initiate PrEP. Given that we have proposed collecting 54 more participants per site (162 total) than is required to estimate our most complex model (see Model 1b in Section 3C.3.10), we believe we will be fully powered to test this model, even with a high rate of PrEP adoption. While contamination of the control group in our pilot study was rare (only one control participant reported using a HBST), we will also track **where** each participant tested (at home, in person) in quarterly surveys. If contamination is significant, we will employ methods aimed at reducing this bias, including adding indicators of contamination as covariates or bootstrapping. To evaluate Aim 1(b), we will generate variables reflecting whether participants received testing for other STIs or risk reduction counseling during each of the four 3-month intervals of the study period. Similar GEE models will be estimated for these outcomes with time period, condition, and site as predictors, to test whether the odds of receiving each service differ across these factors. To evaluate Aim 2, we will code variables indicating whether participant reports or clinic records reflect participants having consulted with a medical provider about PrEP and/or received a PrEP prescription any time across the study period. Factorial logistic regression with study site, condition, and their interaction will be entered as predictors of this outcome, to test whether the odds of having received consultation and/or a PrEP prescription differ across each of the study sites and conditions. Overall, data from those who drop out or withdraw from the study will be used in these analyses, in intent-to-treat (ITT) fashion. Similarly, we will assume values of zero for all outcomes (i.e., non-receipt of testing or services) when quarterly assessments are missing but participants are retained in the study. Depending on the degree of missing assessments, we will use multiple imputation for these values, since data from missing assessments will likely be missing not at random.

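### If used, the contamination covariate would put part of the HIV-testing outcome on the right-hand side of the Aim 1(a) models and could bias the arm contrast

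*Combined protocol and SAP*

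**What the plan says.** Section B.4, Planned Analyses, describes a first Aim 1(a) model that asks if "rates of having completed any HIV test over the 12 month study period (assessed via self-report and/or clinic records) differ by study condition". The second is a GEE "specifying whether participants tested during each 3-month study period as the focal outcome". Neither outcome is limited to tests by the assigned route.

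The subsection Quarterly online questionnaires describes contamination as "the extent to which those assigned to the control condition used a HBST or those in HBST conditions tested at a clinic". Planned Analyses notes that in the pilot "only one control participant reported using a HBST", and then gives the remedy: "If contamination is significant, we will employ methods aimed at reducing this bias, including adding indicators of contamination as covariates or bootstrapping".

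The plan does not say what level of contamination triggers this step, whether the indicator is coded per person or per quarter, or which estimate is the Aim 1(a) result once the covariate has been added. Its intent-to-treat sentence concerns data from participants who drop out or withdraw, and does not bear on this covariate.

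**The concern.** A covariate is meant to explain variation in the outcome from outside it. Here the proposed covariate is one way of having the outcome: a control participant who used a home kit has tested, and so has a home-kit participant who went to a clinic. Adding the flag sets confirmed testers aside, in whatever proportion each arm crossed over, and compares the arms on those who remain. That is no longer the randomised comparison.

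The comparison affected is the main HIV-testing result of the trial. The choice would be made in Year 5, when cross-over by arm can be seen, against an undefined trigger.

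**Working it through.** The plan gives no figure for this adjustment, so there is none to reproduce.

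**Inputs from the documents.** Pilot any-test rates (B.1): eTEST 96%, standard HBST 90%, control 62%. Pilot size: "we enrolled 73 participants". Total sample: 2000.

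**Assumptions.** Equal allocation, which gives 2000/3, or about 667 per arm. An equal split of the pilot, which gives 73/3, or about 24 controls, so one control using a kit is 1/24, or about 4%. All other cross-over shares below are illustrative, because the documents give none.

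**Step 1: what the model estimates.** Let p be the any-test rate in an arm and c the share flagged. Every flagged participant has outcome = 1, so the flag's coefficient runs to infinity (quasi-complete separation) and flagged participants carry no information on the arm effect. The arm odds ratio becomes

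adjusted OR = [(p1 − c1)/(1 − p1)] / [(p0 − c0)/(1 − p0)] = unadjusted OR × (1 − c1/p1)/(1 − c0/p0).

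The multiplier is 1 when c1/p1 = c0/p0, that is, when the flagged share of testers is equal in the two arms.

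**Step 2: check by fitting.** In one simulated trial (667 per arm, 70% tested in both arms, 20% versus 4% flagged), 157 participants were flagged and none of them was untested. The flag's coefficient was 25.0 with a standard error of about 17,000. The arm coefficient was −0.124 (SE 0.122), identical to a fit that leaves out everyone flagged.

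**Step 3: size.** Unadjusted eTEST to control: (0.96/0.04)/(0.62/0.38) = 14.7. Unadjusted eTEST to standard: (0.96/0.04)/(0.90/0.10) = 2.67.

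| Comparison | p1, p0 | c1, c0 | Unadjusted OR | Multiplier | Adjusted OR |
|---|---|---|---|---|---|
| eTEST to control, only control kit use flagged | 0.96, 0.62 | 0, 0.04 | 14.7 | 1.07 | 15.7 |
| Same, more control kit use | 0.96, 0.62 | 0, 0.20 | 14.7 | 1.48 | 21.7 |
| eTEST to control, wider definition | 0.96, 0.62 | 0.10, 0.04 | 14.7 | 0.96 | 14.1 |
| Same, more clinic testing | 0.96, 0.62 | 0.40, 0.04 | 14.7 | 0.62 | 9.2 |
| eTEST to standard, wider definition | 0.96, 0.90 | 0.40, 0.20 | 2.67 | 0.75 | 2.00 |
| No true difference, eTEST to standard | 0.80, 0.80 | 0.40, 0.20 | 1.00 | 0.67 | 0.67 |

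For the last row at 667 per arm, the expected unflagged counts are 266.8 tested and 133.4 untested in eTEST, and 400.2 and 133.4 in standard HBST. The standard error of the log odds ratio is √(1/266.8 + 1/133.4 + 1/400.2 + 1/133.4) = 0.146, so z = ln(0.667)/0.146, or about −2.8.

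**Step 4: type I error.** 20,000 simulated trials, 667 per arm, 70% tested in both arms, 4% of controls flagged:

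| Flagged in the home-kit arm | Adjusted OR | Type I error with flag | Type I error without flag |
|---|---|---|---|
| 4% | 1.00 | 5% | 5% |
| 10% | 0.91 | 12% | 5% |
| 20% | 0.76 | 62% | 5% |
| 30% | 0.61 | 98% | 5% |

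**Step 5: repeated outcome.** This was a pooled logistic fit, which matches the plan's independence working structure, with no true difference, 55% testing per period, and 10% versus 2% flagged per period. The arm odds ratio was 1.00 without the flag and 0.85 with a per-period flag, where every flagged period is a yes. With a per-person ever flag it was 0.86. That flag does not separate the outcome (65% yes among the flagged), but the contrast is still biased.

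**The case against.** **The step is conditional.** It applies only if contamination is judged significant, and covariates are one of two named options. A reader might infer that the adjusted figure will replace the randomised contrast. The documents do not say that, but they do not say that the unadjusted contrast remains the result either.

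**The definition may be narrower.** The remedy follows a remark about contamination of the control group, while the wider definition comes from a passage on what the surveys can track. If only control kit use is flagged, the flag is zero in both home-kit arms and the eTEST-to-standard examples fall away. The defect remains for contrasts with control, because control kit use is also an HIV test, but at the pilot level it is small (14.7 to 15.7).

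**A large eTEST excess of clinic testing is not established.** A reader might infer that the adjustment would create or reverse a difference between eTEST and standard HBST. That needs both the wider definition and shares such as 40% versus 20%, which appear nowhere in the documents. Standard HBST participants also receive a list of testing clinics. PrEP starters have their own covariate, and pilot PrEP initiation in eTEST was 10%. Only about 20 diagnoses are expected trial-wide. The shares could differ, since only eTEST participants get referral calls, but the amount is unknown. Even 40% versus 4% leaves eTEST to control at 9.2.

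**Bootstrapping.** A reader might infer that this second option fails as well. The plan cites outside sources for these methods, and what they propose cannot be checked here, so nothing is concluded about it.

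These objections limit the size and certainty of the harm. They do not change the fact that, under either definition, the flag is a component of the outcome.

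**Conclusion.** The concern holds as a structural flaw in an optional step. In the any-test model, and in the GEE with a per-period flag, the contamination indicator forces the outcome to yes, and the arm odds ratio is multiplied by (1 − c1/p1)/(1 − c0/p0). An ever flag in the GEE is biased without separation.

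Direction and size depend on cross-over that is not yet known. More clinic testing in a home-kit arm pulls its odds ratio against control down, and more home-kit use among controls pushes it up. The shift is about 7% on the odds-ratio scale at the pilot level of control kit use. In the 40% versus 20% illustration it is enough to turn no effect into an apparent effect against eTEST. The per-arm figures assume equal allocation, and the 4% assumes an equal pilot split.

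The point covers HIV-testing outcomes only. For STI testing, counselling and PrEP outcomes the flag arises after randomisation but is not itself the outcome.

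**What to change.** In Planned Analyses, for the HIV-testing outcomes:

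- Delete the option of entering contamination indicators as covariates.
- State that the as-randomised contrast on testing by any route is the Aim 1(a) result whatever the level of cross-over, and that clinic testing in the home-kit arms counts toward the outcome.
- Tabulate tests by route (home, clinic) and arm. The quarterly surveys already ask how and where participants tested.

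An instrumental-variable estimate, with arm as the instrument for kit access, is not a ready substitute. Controls receive reminders and eTEST participants receive counselling calls, so arm can affect testing other than through the kit. The surveys are also not described as recording whether a participant obtained a kit without using it.

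The cost is wording only. The downside is that no contamination-adjusted estimate is reported for testing, so the contrast of home kits with control may be diluted if many controls obtain a kit. The table by route would show how far that happened.

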## B.3 Recruitment Procedures

Ads will be placed with several MSM-oriented “hookup” apps (e.g., Grindr, Scruff, Jack’d) to recruit participants into the study. Ads will display to users who login to the apps within 30 miles of each metro. Clicking on the ad will direct users to a landing page for the eTEST study, where users can learn about the study and its requirements. A brief questionnaire will assess eligibility criteria, and those eligible will then be directed to register for the study, which will involve providing informed consent, basic personal information, and baseline questionnaire data (see Human Subjects for more details about online informed consent). The web app will then randomize participants to one of the three arms. Finally, the web app will then walk participants through downloading the eTEST app from the Google Play or iTunes stores only if they were assigned to the enhanced eTest condition. Access to the eTEST app will be restricted to users registered in the eTEST web portal who are directed specifically from that site. Participants will also be encouraged to keep the app downloaded on their phone throughout the study period and will be encouraged to register any changes in their mailing address or smartphone information (number, phone OS) as soon as possible, either through the eTEST app, web portal, or by notifying study staff.

Once users have registered, staff will conduct a brief introductory call with all participants to ensure that their information is correct and that they understand the study’s requirements. After successfully completing this call, study staff will mark these participants as ‘fully enrolled,’ activating them in the study database.

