## **Measures**

After enrolling, participants will complete a baseline questionnaire assessing demographics, language barriers, immigration status, past HIV/STI testing history, recent use of other prevention/sexual health services, recent sexual behavior, alcohol/drug use, and mental health. These data will be useful for exploring barriers to testing, and changes in these variables over the study period.

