**Power Considerations.** We used past studies and power estimation/ simulation packages in *R*, to determine the sample sizes necessary to detect significant effects in each of the models proposed in 3C.3.8. Relative risk ratios (RRs) were estimated for relevant outcomes (e.g., HIV testing, STI testing) across study conditions in our pilot data, and we used the smallest of these group differences for estimation so as to provide the most conservative estimate of required sample size. For each estimate, we assumed  $\alpha=0.05$ , an observed power of .80, and a small but constant effect (1.2) for study site on each outcome, to ensure that any differences emerging between study sites could be detected. For GEE models, we assumed quarterly measurements ( $T = 4$ ), with relatively independent relationships between repeated data ( $\Phi=0.2$ ). Table 2 summarizes the models, outcomes, parameters, and sample size estimates for each aim. For GEEs, sample size gives the estimated number of participants needed to test condition effects within each site. The sample size required to detect the most complex model with the smallest effects is 246. To account for missing data, we propose collecting 300 MSM at each site.

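### The Aim 1(b) and Aim 2 models name no baseline covariate, although baseline testing history and service use are collected; adjusting for them would add power at almost no cost.

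*Combined protocol and SAP*

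**What the plan says.** All models are in Planned Analyses (section B.4).

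- **Aim 1(a), any HIV test:** "Condition, study site (and their interaction) and other relevant covariates will be entered as predictors". These covariates are not named.
- **Aim 1(b), STI testing and risk reduction counselling in each of four quarters:** "Similar GEE models will be estimated for these outcomes with time period, condition, and site as predictors".
- **Aim 2, PrEP consultation or prescription at any time in the study:** "Factorial logistic regression with study site, condition, and their interaction will be entered as predictors of this outcome". There is no period term, because each man has one outcome.
- **PrEP initiation:** for HIV testing outcomes only, "a covariate reflecting whether a given participant had initiated PrEP (and when, for longitudinal models) will be added to each model". This is a post-randomisation variable and does not reach Aim 1(b) or Aim 2.

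Measures (B.4) lists among the baseline items "past HIV/STI testing history, recent use of other prevention/sexual health services". It gives their purpose as exploring barriers to testing and change over the study, and does not mention adjustment.

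On timing, Measures says "After enrolling, participants will complete a baseline questionnaire". B.3 Recruitment Procedures describes registration as "providing informed consent, basic personal information, and baseline questionnaire data" and places randomisation after that; Procedure in B.4 says the same. B.5 places randomisation after completion of consent and does not mention the questionnaire. C.1.1 places the questionnaire after consent, and formal enrolment after the introductory call.

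**The concern.** For Aim 1(b), recent STI testing and recent service use are, or are close to, baseline versions of the outcomes. Men who used a service before the trial are plausibly more likely to use it during the trial. A model without that information leaves explainable between-person variation in the comparison of arms. What is at stake is power, most of all for STI testing, where the pilot difference is described as only modest, and for comparisons within a site.

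The omission also leaves the choice of covariates open until the Year 5 analysis, when outcome data will be in hand.

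Timing matters because a baseline covariate is safe only if it is recorded before the man knows his arm. Here the arm determines the orientation screens that he sees.

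**Working it through.** **1. The plan's own figures.** Power Considerations assumes alpha 0.05, "an observed power of .80, and a small but constant effect (1.2) for study site on each outcome", T = 4 quarters and a correlation of 0.2 between them. It requires 246 and proposes 300 per site. The surplus reproduces: 300 − 246 = 54, and 3 × 54 = 162. The 246 itself cannot be checked, because the effect sizes are in a table that is not in the available text. No baseline covariate enters the stated assumptions.

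**2. Inputs for the gain.** The documents supply T = 4 and the between-quarter correlation of 0.2. They give no correlation between a baseline item and any outcome, so that input is assumed and varied.

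**3. Aim 1(b).** With between-quarter correlation ρ and unit variance per quarter, the variance of a man's four-quarter mean is (1 + 3ρ)/4. If baseline correlates with each quarter at b, the share of that variance explained is R² = b² / [(1 + 3ρ)/4]. The equivalent gain in participants is 1/(1 − R²) − 1.

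At ρ = b = 0.2: (1 + 0.6)/4 = 0.40; R² = 0.04/0.40 = 0.10; gain = 1/0.90 − 1 = 11.1%.

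Taking b = ρ throughout (exchangeable, baseline included):

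| ρ = b | R² | Gain |
|---|---|---|
| 0.10 | 0.031 | 3.2% |
| 0.15 | 0.062 | 6.6% |
| 0.20 | 0.100 | 11.1% |
| 0.30 | 0.189 | 23.4% |
| 0.35 | 0.239 | 31.4% |

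This formula is a linear approximation. It was checked by simulating binary outcomes (1,500 replicates) with an independence-working GEE and cluster-robust errors, with and without a binary baseline covariate. The gain, taken as the squared ratio of mean z statistics less one, was 3.0% at correlation 0.093, 13.8% at 0.216 and 24.7% at 0.307. This agrees with the table.

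The 11.1% corresponds to about 222 of 2000 men (B.4), or 100 of the 900 implied by 300 at each of three sites (Power Considerations). The two planned totals conflict and need reconciling separately.

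**4. Aim 2.** There is one yes/no outcome per man, so R² = r² and the four-quarter formula does not apply.

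| r | Gain = 1/(1 − r²) − 1 |
|---|---|
| 0.1 | 1.0% |
| 0.2 | 4.2% |
| 0.3 | 9.9% |

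To show what such correlations mean, assume a baseline marker held by 20% of men and outcome rates of 10% and 25%. An odds ratio of 2 gives correlations of 0.096 and 0.130 (gains of 0.9% and 1.7%). An odds ratio of 4 gives 0.211 and 0.272 (gains of 4.7% and 8.0%). Gains above about 10% need a very strong marker: an odds ratio of 8 gives 12.3% and 20.3%.

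**5. Timing.** B.3 and Procedure in B.4 both give the order consent, baseline data, randomisation. Measures puts the questionnaire after enrolling. If enrolment has the meaning in C.1.1 (after the introductory call), that is after randomisation. However, Design Considerations speaks of a staff call that follows enrolment, which is the opposite usage. B.5 fixes randomisation only relative to consent. The order is therefore unclear rather than shown to be wrong.

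**The case against.** **Covariates may be intended.** The Aim 1(b) models are called similar to the Aim 1(a) GEE, which includes relevant covariates, and the predictor lists are loosely written throughout. This is a fair reading, but it does not rescue the plan, because the Aim 1(a) covariates are never named. On either reading no baseline covariate is prespecified for Aim 1(b) or Aim 2.

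**The unadjusted analysis is valid, and power may be ample.** Both parts have force. Randomisation protects the unadjusted comparison, and 666 per site is 2.7 times the stated 246 (666/246). A reader might infer that these aims are underpowered; the documents do not show that.

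**The benefit may be small here.** Men who tested for HIV in the last 12 months are excluded, which may make recent STI testing at baseline uncommon. Scoring missed surveys as zero may further weaken the link between baseline and outcome. Both points stand, and they argue for the lower part of the ranges.

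Four stronger readings should be resisted:

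- **One large figure for both aims.** A reader might put a baseline correlation of 0.4 beside the between-quarter 0.2 and obtain R² = 0.16/0.40 = 0.40, or 67% more participants. Nothing in the documents supports baseline predicting a quarter better than quarters predict each other, and the formula does not fit Aim 2.
- **A smaller standard error for the odds ratio.** In a logit model, adjustment moves the estimand to a conditional odds ratio. The gain is in the test, or in a standardised effect.
- **PrEP consultation as a weak-effect outcome.** The pilot rates were 25% in the eTEST arm and 4% in control, which is not among its smallest differences.
- **The questionnaire follows allocation.** Two sections say that it precedes it.

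**Conclusion.** The point holds as a missed, nearly free gain in power and a gap in prespecification. It is not a threat to validity.

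For Aim 1(b) the best-anchored figure is about 11% more participants' worth of power. It assumes that baseline correlates with each quarter as strongly as the plan assumes quarters correlate with each other; the range is about 3-31% for exchangeable correlations of 0.10-0.35. For Aim 2 it is about 1-10% for correlations of 0.1-0.3, since no baseline item is an earlier version of the outcome. Both ranges rest on assumed correlations, and the eligibility rule may pull them down.

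The timing point is an ambiguity of wording that must be settled before baseline answers are used as covariates. The change should be made.

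**What to change.** 1. **Aim 1(b):** prespecify in each GEE the baseline value of the same service: recent STI test for STI testing, and recent risk reduction counselling or service use for counselling.
2. **Aim 2:** add baseline service use and HIV/STI testing history to the logistic model.
3. **Reporting:** give a standardised (marginal) effect for each arm comparison beside the conditional odds ratio.
4. **Timing:** reconcile Measures and B.5 with B.3 and Procedure in B.4, so that the baseline questionnaire is clearly submitted before the web app releases the allocation.

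The cost is SAP wording, plus confirmation that the web app enforces the order already described in B.3. No extra data or recruitment is needed. The downside is that the odds ratios become conditional on baseline use, which is why the standardised effect should accompany them.

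### Missed quarterly surveys are scored zero without first using the next survey's look-back answer, and a later switch to multiple imputation is left open

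*Combined protocol and SAP*

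**What the plan says.** Planned Analyses (section B.4) makes three statements about missing outcome data.

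- **Withdrawn participants:** "data from those who drop out or withdraw from the study will be used in these analyses", on an intent-to-treat basis. No value is given for quarters after withdrawal.
- **Retained participants who miss a survey:** the rule is "values of zero for all outcomes (i.e., non-receipt of testing or services) when quarterly assessments are missing but participants are retained in the study".
- **The alternative:** "Depending on the degree of missing assessments, we will use multiple imputation for these values". The reason the plan offers is "since data from missing assessments will likely be missing not at random". No threshold, imputation model or primary analysis is named.

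Under Quarterly online questionnaires, the recall periods differ by item. On HIV testing: "These surveys will assess HIV testing since the last study assessment". On other prevention services: "whether they received these services since the last survey". On PrEP, the item asks "whether participants consulted with a medical provider about PrEP in the last month", and the prescription question follows from it. The section does not say whether the last survey means the last one completed or the last one scheduled.

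Under Procedure, missing two surveys in a row counts as withdrawal. That section pays for five quarterly surveys, whereas Planned Analyses builds four 3-month intervals.

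**The concern.** There are two linked problems.

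**The switch is open.** Zero-filling and standard imputation are right under different mechanisms. Zero-filling is right if people who miss a survey did not test. Standard multiple imputation assumes data missing at random, so it does not address the reason the plan itself gives for using it. If survey completion differs between arms, the two rules can err in opposite directions, and a choice made after the extent of missingness is known could shape the conclusion.

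**Information is discarded.** A retained participant who skips a survey will complete the next one, unless the skipped survey was the last. If that next survey asks about the period since the last completed survey, it covers the skipped quarter. The plan does not say that this answer takes precedence over an assumed zero.

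The quarterly GEE models for repeat HIV testing, STI testing and risk reduction counseling are the most exposed. An any-time outcome needs only one positive report, so it is affected mainly if withdrawn participants count as non-testers.

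**Working it through.** **The plan's own allowance.** Power Considerations requires 246 and plans 300 per site because of missing data: 300 − 246 = 54, and 3 × 54 = 162, as Planned Analyses states. This implies an allowance of 54/300 = 18%. Extra participants protect precision but do not remove bias from a fill-in rule.

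**What look-back can reach.** Two misses in a row mean withdrawal, so every skipped survey of a retained participant, except the final one, is followed by a completed survey. In the simulation below, with 10% missing and four surveys, about 74% of the surveys that would be zero-filled can be recovered this way.

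**Inputs.** From the documents: 2000/3 ≈ 666 per arm (equal allocation assumed), T = 4, correlation 0.2, α = 0.05 (taken as two-sided). Assumed: no true effect, 50% testing per quarter, 10% v 20% of surveys missed in two arms.

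**Mechanisms.** U: missingness is unrelated to testing. D: missed quarters have a 25% testing rate. For D with missing share m, P(miss | tested) = 0.5m and P(miss | not tested) = 1.5m.

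**Hand check, before the extra quarters lost through withdrawal.**
- Zero-fill under U: 0.5 × 0.90 − 0.5 × 0.80 = 0.45 − 0.40 = 5.0 points of false difference.
- Completed surveys only under D: the observed rate is 0.5(1 − 0.5m)/(1 − m). At m = 0.10 this is 0.475/0.90 = 52.8%. At m = 0.20 it is 0.45/0.80 = 56.3%. The false difference is −3.5 points.

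**Simulation.** 4,000 runs per scenario, beta-binomial quarterly outcomes, independence GEE with robust standard errors. Withdrawal runs from the first of two consecutive misses. Look-back is assumed accurate and assigned to the right quarter. A positive bias favours the arm with fewer missed surveys. Repeat runs differ by a point or two.

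| Rule (10% v 20% missing) | U: false positives (bias) | D: false positives (bias) |
|---|---|---|
| Zero-fill, withdrawn quarters excluded | 53% (+3.4 points) | 5% |
| Zero-fill, withdrawn quarters also zero | 94% (+5.8 points) | 48% (+3.2 points) |
| Completed surveys only (proxy for missing-at-random imputation) | 5% | 53% (−3.7 points) |
| Look-back, then zero; withdrawn quarters excluded | about 9% | 8–10% |
| Look-back, then zero; withdrawn quarters zero | 59% | 23% |

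The 5% in the first row under D is a cancellation. Zeros pull the high-missing arm down, while excluding withdrawn quarters removes mostly non-testers from that arm.

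At 10% v 15% the effects are smaller. Zero-fill with withdrawn quarters excluded gives 19% under U (+1.8 points), and completed surveys only gives 16% under D (−1.7 points). With equal 10% missing, every rule gives about 5%.

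**Surveys and intervals.** The payment total confirms that five quarterly surveys are meant: 25 × (1 + 5) + 50 + 50 = 250. Which survey supplies which of the four intervals is not stated.

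**The case against.** The strongest reply is that the plan has a rule. Zero is a plain default for retained participants. The zero rule follows the intent-to-treat sentence and opens with a linking word, so zeros may be meant for withdrawn participants too. That stands in part: it would be wrong to say that missing surveys have no rule. But the zero sentence is limited to those retained, and the move to imputation has no condition that could be checked.

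Second, the arm gap is assumed. Reminders, staff follow-up and payments are the same in all arms, and the pilot's 94% completion is pooled and comes from monthly surveys. This stands. Only eTEST has the app and counselor calls, which makes a gap plausible but does not show one.

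Third, the plan introduces the quarterly HIV-testing model as exploring regular testing. Yet Aim 1(a) includes follow-up testing, and Aim 1(b) is evaluated with the same type of model.

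Fourth, the plan names no imputation model, so one suited to data missing not at random is possible. It is not stated.

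Two stronger readings are tempting and are not supported:

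- A reader might set these biases against the pilot's 54% v 46% for standard HBST and control. Those are rates of testing in both of two periods. At correlation 0.2, P(both) = 0.8p² + 0.2p, so they correspond to about 71% and 64% per quarter. The per-quarter biases above cannot be read as a share of that 8-point gap.
- A reader might infer that clinic records, which cannot show a home test, tilt the comparison toward control even with equal completion. But "assessed via self-report and/or clinic records" is attached to the any-test outcome. Planned Analyses names clinic records again for PrEP but does not clearly bring them into the quarterly models. Records are sought from clinics named in the surveys, releases are optional, and no retrieval rate is given.

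**Conclusion.** The concern holds in a limited form. The plan states a default, leaves the departure from it undefined, and does not use look-back answers that its own questionnaire can provide. Under the assumed 10% v 20% gap, the false difference ranges from +5.8 to −3.7 points according to rule and mechanism, with false-positive rates from about 5% to about 94%. Using look-back first and excluding withdrawn quarters brings this to about 8–10% under both mechanisms. It does not repair zeros assigned after withdrawal, which is why that rule must be set separately.

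These figures illustrate sensitivity and do not forecast this trial's error rate. They depend on an arm gap that no document shows, on a 50% testing rate and on accurate recall. They are not an upper bound on the bias. The case for change is that the improvement is cheap and uses information the surveys already seek.

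**What to change.** 1. **Look-back first.** Before assigning any zero, fill a skipped quarter from the next completed survey, in the same way in all arms. If the surveys can still be changed, word the items to run from the last survey the participant completed, and ask the month of each test so that it can be placed in a quarter. Do not use look-back for PrEP consultation, which is asked for the last month only.
2. **Fix the rules before outcome data are seen.** Delete the condition on the amount of missing data. Name one primary rule for the remaining gaps and one for quarters after withdrawal. Zero-fill or imputation by arm is defensible as primary; if imputation is chosen, give its model. State which of the five surveys supplies which of the four intervals.
3. **Show the sensitivity.** Report survey completion and withdrawal by arm. Add a delta-adjusted (tipping-point) analysis by arm that runs from missing-at-random imputation to zero-fill.

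The cost is SAP text, a little extra analysis and a small wording change to the survey. If the surveys are already in the field, look-back can be used only where the existing wording allows.
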